4.6 Statistical Methods

All statistical processing will be performed using SAS® unless otherwise stated.

Continuous variables will be summarized descriptively using number of subjects (n), mean, standard deviation (SD), minimum, median, and maximum. Categorical variables will be summarized descriptively using frequency counts and percentages.

Analyses presented for the Per-Protocol (PP) will be considered primary.

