4.5.1.2 Surgical Reintervention

Subjects will be asked to indicate whether any of their adverse events required a surgery or procedure. The rate of surgical reintervention due to treatment failure will be evaluated throughout all assessment timepoints. Surgical reintervention for the treatment of HMB includes the following procedures:

- a) Hysterectomy (abdominal, vaginal, laparoscopic)
- b) Myomectomy (abdominal, vaginal, laparoscopic, hysteroscopic)
- c) Uterine artery embolization
- d) Magnetic resonance-guided focused ultrasound (MRgFUS) or similar focused ultrasound treatment
- e) Endometrial ablation (nonresectoscopic, hysteroscopic)

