4.6.1 Analysis Populations

The safety population will be comprised of subjects who received study treatment.

The Per-Protocol population (PP) will be comprised of subjects in the safety population who have a post baseline assessment, an evaluable hysteroscopy at Baseline and Week 6 follow-up and completed the Week 6 follow-up visit.

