4.6.4 Efficacy Analyses

Efficacy evaluations will be summarized descriptively, by visit.

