4.6.4.1 Primary Efficacy Analysis

Final Outcome will be presented using frequency counts and percentages for No New Adhesions at Week 6 and Adhesions at Week 6. Specifically, Final Outcome will be determined based on agreement in hysteroscopy evaluation between 2 out of the 3 Independent Readers. The ESH score will also be summarized using descriptive statistics for baseline (both Investigator and Independent Reader) and the Week 6 visit (Independent Reader only). The Final Outcome assessment will be done for both the Safety and Per Protocol populations. In either population:

- For subjects whose final 6-week hysteroscopy determination per agreement by two out of three Independent Readers shows Adhesion(s):
 - o Final Outcome is **New Adhesion** if the final baseline hysteroscopy determination per agreement by two out of three Independent Readers showed No Adhesion.
 - o Final Outcome is **Undetermined** if the final baseline hysteroscopy determination per agreement by two out of three Independent Readers showed Adhesion.
 - o Final Outcome is **Undetermined** if there were no evaluable hysteroscopy at baseline.
- For subjects whose final 6-week hysteroscopy determination per agreement by two out of three Independent Readers shows presence of No Adhesion(s):
 - Final Outcome is No New Adhesion.

In addition, a reader agreement analysis will be presented using frequency counts and percentages for the Baseline and the Week 6 visits.

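### Surgical reintervention is a primary efficacy variable with no stated analysis population; under the per-protocol default, a hysterectomy for heavy bleeding before the Week 6 hysteroscopy drops out of its own rate

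*SAP*

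**What the plan says.** Section 4.5.1 has two primary efficacy variables: new intrauterine adhesions at six weeks (4.5.1.1) and surgical reintervention (4.5.1.2). For the second, the SAP states: "The rate of surgical reintervention due to treatment failure will be evaluated throughout all assessment timepoints". It continues "Surgical reintervention for the treatment of HMB includes the following procedures", and hysterectomy is item a) of that list.

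The analysis text is as follows.

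- **4.6:** "Analyses presented for the Per-Protocol (PP) will be considered primary". Categorical variables are summarised by counts and percentages.
- **4.6.1:** PP members are treated women with a post-baseline assessment and "an evaluable hysteroscopy at Baseline and Week 6 follow-up and completed the Week 6 follow-up visit". The other population is broader: "The safety population will be comprised of subjects who received study treatment".
- **4.6.4:** one general sentence, "Efficacy evaluations will be summarized descriptively, by visit".
- **4.6.4.1:** covers the adhesion outcome only, and names two populations for it: "The Final Outcome assessment will be done for both the Safety and Per Protocol populations".
- **4.6.4.2:** covers Overall Treatment Effect and Subject Satisfaction only.

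Table 1 schedules one follow-up visit, at 6 weeks, and collects surgical reintervention there. A footnote to that row deals with subjects who have a hysterectomy.

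**The concern.** One of the two primary variables has no analysis paragraph, denominator or population of its own, although both secondary variables have a paragraph each. The PP-primary default then applies because nothing else does. That default suits the adhesion outcome, which cannot be assessed without the hysteroscopy. It does not suit reintervention, because one of the counted events makes the qualifying examination impossible. The population is then selected on the outcome, and the reported rate of treatment failure can be too low. In a study of at most 60 women, a single case can decide whether the primary reintervention rate is zero.

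**Working it through.** The SAP states no reintervention rate and no power calculation, so there is no figure of its own to reproduce. The check has two parts: which rule applies, and what that rule does to the rate.

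**Which rule applies**

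1. Reintervention sits under 4.5.1, so it is primary. Secondary variables begin at 4.5.2.
2. Within 4.6.4, only the general descriptive sentence reaches it, and that sentence names no population.
3. The statement that both populations are used is limited to the adhesion Final Outcome.
4. The PP-primary sentence in 4.6 is the only population rule left. That it governs reintervention is an inference from a default, but the SAP offers no competing rule.
5. PP needs an evaluable Week 6 hysteroscopy. A hysterectomy before it rules this out. With a single follow-up visit at 6 weeks, PP can count a hysterectomy within scheduled follow-up only if it falls after that hysteroscopy.

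The other listed procedures need not exclude a woman. A hysterectomy for a reason other than HMB removes no event from the numerator.

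**Effect on the rate**

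- *N* = women treated. 4.6.8 allows up to 60; 40 is an assumed smaller enrolment.
- *h* = hysterectomies for HMB before the Week 6 hysteroscopy (assumed).
- *k* = women with another listed procedure who remain PP-evaluable (assumed).
- *m* = women not PP-evaluable for unrelated reasons (assumed).

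PP rate = k / (N − h − m). All-treated rate = (h + k) / N.

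| N | h | k | m | PP rate | All-treated rate |
|---|---|---|---|---|---|
| 60 | 0 | 0 | 0 | 0/60 = 0% | 0/60 = 0% |
| 60 | 1 | 0 | 0 | 0/59 = 0% | 1/60 = 1.67% |
| 60 | 2 | 0 | 0 | 0/58 = 0% | 2/60 = 3.33% |
| 60 | 3 | 0 | 0 | 0/57 = 0% | 3/60 = 5.00% |
| 40 | 1 | 0 | 0 | 0/39 = 0% | 1/40 = 2.50% |
| 40 | 2 | 0 | 0 | 0/38 = 0% | 2/40 = 5.00% |
| 40 | 3 | 0 | 0 | 0/37 = 0% | 3/40 = 7.50% |
| 60 | 1 | 1 | 0 | 1/59 = 1.69% | 2/60 = 3.33% |
| 60 | 0 | 1 | 4 | 1/56 = 1.79% | 1/60 = 1.67% |

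Whatever value *h* takes, it never enters the PP numerator. The last row shows that PP can also be slightly the higher of the two, when unrelated exclusions shrink its denominator and no such hysterectomy occurs.

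For scale, exact (Clopper-Pearson) 95% limits are: 0/59, upper limit 6.06%; 1/60, 0.04% to 8.94%; 0/39, upper limit 9.03%; 1/40, 0.06% to 13.16%.

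**Whether anything else restores the event**

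- Section 4.6.2 reports reasons for exclusion from a population. That may reveal the case but is not a reintervention rate.
- Section 4.6.9.2 rules out imputation unless otherwise specified.
- The adverse event tables are not a reliable fallback. NOTE 1 under the adverse event definition (4.5.4.1.1) leaves out elective reintervention for HMB.

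**The case against.** The case for leaving the SAP alone has five parts.

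- **The PP sentence ranks analyses and does not restrict them.** A Safety-population table is not forbidden. This is correct, but none is specified for this variable, and PP would still be the primary result.
- **The format is not wholly missing.** The general sentence in 4.6.4 and the categorical rule in 4.6 imply counts and percentages by visit. This also stands. What is missing is the population and denominator, which is where the problem lies.
- **The effect needs a specific event for which the SAP gives no rate.** It needs a hysterectomy, for HMB, before the Week 6 hysteroscopy. This stands in full: the undercount is zero without a case, the scenarios with two or three cases and with N = 40 are illustrations only, and the exact intervals overlap widely.
- **A case would probably be noticed, and little depends on it.** Disposition would show the exclusion, and operative and pathology reports go to the sponsor. The stated objective concerns adhesions, and the study is exploratory without a test. This limits the consequence but does not put the event back into the rate.
- **An all-treated percentage has its own bias.** It counts women of unknown status as having had no reintervention. This is fair, and it is why the unknown count belongs beside the rate.

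**Conclusion.** The concern holds. The SAP fixes no population for a primary variable, and the only rule that reaches it excludes women because of one of the events it is meant to count. The size is conditional: with 60 treated and no other exclusions or procedures, each such hysterectomy adds about 1.7 percentage points to the all-treated rate and nothing to the PP rate. All event counts are assumptions. Because the study is descriptive, no test or decision threshold is affected; the damage is to the reported estimate of treatment failure. It should be corrected, but it does not threaten the adhesion analysis.

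**What to change.** 1. In 4.6, exempt surgical reintervention (4.5.1.2) from the PP-primary rule and name the Safety population as primary for it. Leave all other endpoints as they are.
2. In 4.6.4, add one sentence: report the number and percentage of women in the Safety population with at least one procedure listed in 4.5.1.2 performed for HMB, and show beside it the number whose reintervention status is unknown. An exact confidence interval and a second rate among women of known status are optional; the second rate would meet the point about unknown status.

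The cost is one clause, one sentence and one table. Table 1 already schedules the data. The downside is a denominator that differs from that of the PP adhesion table, which a table footnote can explain.

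A separate, lower-weight point is to state which source defines the endpoint. Section 4.5.1.2 asks whether adverse events required surgery, NOTE 1 in 4.5.4.1.1 takes elective reintervention for HMB out of the adverse events, and Table 1 has its own reintervention item. These three need to be reconciled.

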4.6.3 Demographic and Baseline Characteristics

Subject demographic and baseline characteristics will be summarized descriptively for the PP and safety populations. Demographic and baseline variables will include variables such as age, height, weight and BMI. OB-GYN history variables will also be summarized. Demographic and baseline variables as well as OB-GYN history variables will be summarized using descriptive statistics.

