4.6.4.2 Other Efficacy Analysis

4.6.4.2.1 Overall Treatment Effect (OTE)

OTE will be summarized using descriptive statistics.

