4.6.4.2.2 Subject Satisfaction

Subject Satisfaction will be summarized using descriptive statistics.

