4.6.7.2 EuroQOL EQ-5D

The EuroQOL EQ-5D will be summarized by visit using descriptive statistics.

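### By default, the primary summaries of OTE and satisfaction leave out women who answered at Week 6 but lack an evaluable hysteroscopy; the set for EQ-5D and the recovery diary is left open

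*SAP*

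**What the plan says.** The general part of SAP section 4.6 ranks the populations in one sentence: "Analyses presented for the Per-Protocol (PP) will be considered primary". It mentions no endpoint and makes no exception.

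Section 4.6.1 defines two sets:

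- Safety: "The safety population will be comprised of subjects who received study treatment".
- PP: members of the Safety set who have a post-baseline assessment, "an evaluable hysteroscopy at Baseline and Week 6 follow-up and completed the Week 6 follow-up visit".

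Besides the disposition counts, two analyses are given their sets by name, and each uses both. In 4.6.4.1: "The Final Outcome assessment will be done for both the Safety and Per Protocol populations". In 4.6.3: "Subject demographic and baseline characteristics will be summarized descriptively for the PP and safety populations".

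The patient-reported outcomes are given none. For OTE (4.6.4.2.1): "OTE will be summarized using descriptive statistics". For satisfaction (4.6.4.2.2): "Subject Satisfaction will be summarized using descriptive statistics". For EQ-5D (4.6.7.2): "The EuroQOL EQ-5D will be summarized by visit using descriptive statistics". The recovery diary (4.6.7.3) is treated in the same way.

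**The concern.** Requiring evaluable hysteroscopies at both visits makes sense for new adhesions, because that outcome compares the two examinations. It has no connection with a woman's ability to say whether her symptoms improved or whether she is satisfied.

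If the PP rule carries over, an observed answer is left out of the primary table because a video was missing or could not be read. The plan foresees such women. Section 4.6.4.1 has an outcome category for those without an evaluable baseline examination, and Table 1 shows the baseline hysteroscopy as part of ordinary care.

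Two things are at stake. The summary describes a group selected on something irrelevant to the question, and a small study loses answers that it has already collected. Where the set is not fixed at all, two programmers could also produce different primary tables from the same data.

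**Working it through.** **Step 1: the rules side by side**

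| Outcome | SAP analysis section | Parent heading | Set named | What follows |
|---|---|---|---|---|
| Adhesion Final Outcome | 4.6.4.1 | Efficacy Analyses | PP and Safety | PP leads, by 4.6 |
| OTE | 4.6.4.2.1 | Efficacy Analyses | none | PP by default |
| Satisfaction | 4.6.4.2.2 | Efficacy Analyses | none | PP by default |
| EQ-5D | 4.6.7.2 | Safety Analyses | none | PP or Safety, not fixed |
| Recovery diary | 4.6.7.3 | Safety Analyses | none | PP or Safety, not fixed |

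For OTE and satisfaction, the only priority rule that can apply is the sentence in 4.6. The abbreviation list includes a full analysis set, but 4.6.1 does not define one.

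For EQ-5D and the diary, the heading suggests the Safety set. The SAP never assigns that set to section 4.6.7.

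**Step 2: who would be left out**

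- OTE and satisfaction are collected at the six-week visit (Table 1). Women who miss that visit generally have no answer under either set. The women who matter are those who answered but have no evaluable hysteroscopy at baseline or at Week 6.
- The diary covers the first two weeks (4.5.4.3). If PP applied, a complete diary would be excluded because of a visit missed, or a video found unreadable, a month later.

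**Step 3: possible size (illustration)**

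The SAP gives no satisfaction rate and no rate of non-evaluable examinations, so there is no planned figure to reproduce. Only N = 60 (the upper limit in 4.6.8) comes from the document. The assumptions are that all 60 women answer, that 90% of the PP set are satisfied, and that 50% to 90% of the excluded women are satisfied.

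- All-responder rate = (n_PP × 0.90 + n_out × p_out) / 60
- Shift = (n_out / 60) × (0.90 − p_out)
- Precision, as an approximate 95% half-width = 1.96 × √(0.90 × 0.10 / n)

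| Not evaluable | n_PP | n_out | All-responder rate, p_out = 50% | p_out = 70% | p_out = 90% | Half-width, PP |
|---|---|---|---|---|---|---|
| 5% | 57 | 3 | 88% | 89% | 90% | 7.8 points |
| 10% | 54 | 6 | 86% | 88% | 90% | 8.0 points |
| 20% | 48 | 12 | 82% | 86% | 90% | 8.5 points |
| 30% | 42 | 18 | 78% | 84% | 90% | 9.1 points |

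With all 60 women the half-width is 7.6 points.

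Worked for the last row: (42 × 0.90 + 18 × 0.50) / 60 = (37.8 + 9.0) / 60 = 78%. The shift is 18/60 × 0.40 = 12 points. When p_out equals 90%, the shift is zero and only precision is lost.

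The sign is open as well. If all 18 excluded women were satisfied, the rate would be (37.8 + 18) / 60 = 93%, and the PP figure would be 3 points too low.

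**The case against.** The strongest reply is that the sentence in 4.6 only ranks results where a PP version exists. Adhesions and baseline characteristics are presented for both sets, so the sentence has a natural job there, and nothing says that every analysis is presented for PP. That is fair. A reader might infer that PP is primary for every analysis in the plan, and the text does not go that far. For OTE and satisfaction, however, the efficacy heading offers no other set, and this sentence is the only default available.

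Second, a reader might infer that EQ-5D and recovery times certainly lose these women. The document does not support that. Both are classed as safety variables (4.5.4.2, 4.5.4.3) and analysed under Safety Analyses, where using all treated women is an equally natural reading. What stands is that the set is not fixed.

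Third, calling PP primary does not bar a Safety-set table, and 4.6.2 requires the reasons for exclusion to be reported. The exclusion therefore concerns the primary result. The data are not lost, and the number of women outside PP would be visible.

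Fourth, a reader might infer that the selection favours satisfied women, on the thought that those with a poor experience decline the second hysteroscopy. The SAP offers no evidence for this. A baseline video that cannot be read arises before treatment and points in no particular direction.

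**Conclusion.** The point holds in limited form. As written, the primary summaries of OTE and satisfaction are restricted by default to women with evaluable hysteroscopies at both visits, a condition that these outcomes do not need. For EQ-5D and the diary, the plan leaves the choice between PP and Safety open.

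The number of women affected and the direction of any bias are unknown. Under the assumed rates, the effect on a percentage runs from nil to 12 points, and the 12 points need both 30% non-evaluable and a 40-point difference in satisfaction. The loss of precision is certain whenever anyone who answered is excluded, but it is small: in the table, at most 9.1 against 7.6 points.

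Severity is minor. The stated objective concerns adhesions only, none of these four outcomes is primary, all are summarised descriptively, and 4.6.8 calls the study exploratory and unpowered. The adhesion result is not touched.

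**What to change.** Add to SAP section 4.6, after the sentence on the primary population:

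> The PP-primary rule does not apply to OTE, subject satisfaction, EQ-5D and the recovery diary; these are summarised primarily in the Safety population using all women with the respective data, with PP results supportive.

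Wording the change as an exemption matters. Limiting the rule to adhesions alone would remove the only default for surgical reintervention, which 4.5.1.2 lists as a primary efficacy variable. The exemption leaves the default for the adhesion Final Outcome and all other analyses as it is.

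The cost is one sentence and no new data. Denominators will differ between the adhesion tables and the questionnaire tables, so each table should show its n, and EQ-5D should show it by visit.

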4.6.1 Analysis Populations

The safety population will be comprised of subjects who received study treatment.

The Per-Protocol population (PP) will be comprised of subjects in the safety population who have a post baseline assessment, an evaluable hysteroscopy at Baseline and Week 6 follow-up and completed the Week 6 follow-up visit.

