3. STUDY OBJECTIVES

The objective of this study is to document the presence or absence of newly formed intrauterine adhesions after treatment with the Sonata System when used in women with submucous and/or transmural fibroids in accordance with product labeling.

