4.2 Selection of Study Population

4.2.1 Inclusion Criteria

- 1) Have selected Sonata for treatment of fibroids in the presence of heavy menstrual bleeding
- 2) Presence of at least one submucous myoma (type 1, type 2) or transmural fibroid (type 2-5)
- 3) Are \geq 18 years of age at the time of enrollment
- 4) Willing and able to read, understand, and sign the informed consent form and to adhere to all study follow-up requirements

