4.2.2 Exclusion Criteria

- 1) Preexisting adhesions within the endometrial cavity as indicated by an ESH score \geq I as determined by the investigator
- 2) One or more Type 0 fibroids and/or endometrial polyps of any size
- 3) Any reason for which, in the opinion of the Investigator, the individual study patient is not appropriate or suitable for participation in this study

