4.6.5 Procedure Summaries

The following procedure related information will be summarized using descriptive statistics:

- LOS (start of procedure to discharge)
- Time admission to discharge
- Procedure time (time of device insertion to removal)
- Patient Side (left, right, midline)
- Location (anterior, posterior, midline)
- Location (fundal, body, LUS, cornual, other)
- Fibroid type
- FIGO type
- Size of fibroids treated (visualized and ablated)
- Number of fibroids treated
- Number of fibroids per subject
- Number of ablations per fibroid
- Number of ablations per subject
- Number of ablated fibroids per subject

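### The primary Per-Protocol set does not check eligibility, so women with reader-confirmed adhesions at baseline stay in the adhesion rate and can only lower it or leave it unchanged

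*SAP*

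**What the plan says.** Section 4.6 ranks the analysis sets: "Analyses presented for the Per-Protocol (PP) will be considered primary". Section 4.6.1 builds them in two steps. The base is treatment: "The safety population will be comprised of subjects who received study treatment". The primary set is then cut from it: "The Per-Protocol population (PP) will be comprised of subjects in the safety population who have a post baseline assessment, an evaluable hysteroscopy at Baseline"; the sentence goes on to ask for the same at Week 6 and for a completed Week 6 visit.

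Eligibility is set out elsewhere. Inclusion criterion 2 (4.2.1) asks for "Presence of at least one submucous myoma (type 1, type 2) or transmural fibroid (type 2-5"). Exclusion criterion 1 (4.2.2) bars "Preexisting adhesions within the endometrial cavity as indicated by an ESH score" of I or more, on the investigator's judgement. Exclusion criterion 2 bars "One or more Type 0 fibroids and/or endometrial polyps of any size". The PP definition refers to none of these.

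Section 4.6.4.1 derives the Final Outcome for both the Safety and PP populations from the independent readers' two-out-of-three determinations. If Week 6 shows adhesions, the outcome is New Adhesion only when baseline showed none; it is Undetermined when baseline showed adhesion or was not evaluable. If Week 6 shows no adhesion, the outcome is No New Adhesion, with no reference to baseline.

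**The concern.** A set called Per-Protocol would normally leave out women who did not meet the entry criteria. This one removes only women with missing assessments, so it is an evaluable-completer set under another name. Section 4.6.2 promises the reasons for exclusion from each population, but 4.6.1 supplies no eligibility reason that could appear there.

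This matters most for adhesions already present at baseline. The investigator decides on them at entry, while the outcome uses the independent readers' view of the same baseline examination. Section 4.6.4.1 expressly allows for the readers finding adhesion at baseline in an enrolled woman. Such a woman is not at risk of the event as the SAP defines it, yet nothing takes her out of the primary set.

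The main result is a single proportion in at most 60 women with no comparison arm, so a few such women can move it visibly.

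**Working it through.** The only related figure in the SAP is the sample size of up to 60 (4.6.8). It comes with no rate, precision or power, so there is no calculation to reproduce. The check is one of definitions, followed by illustrations on assumed counts.

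**Step 1. What PP membership requires (4.6.1).**

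| Condition | Kind |
|---|---|
| Received study treatment (through the Safety population) | Exposure |
| Some assessment after baseline | Data availability |
| Evaluable hysteroscopy at Baseline and at Week 6 | Data availability |
| Week 6 visit completed | Data availability |
| Inclusion criterion 2, exclusion criteria 1 and 2 | Not required |

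**Step 2. A PP member with reader-confirmed adhesion at baseline (4.6.4.1).**

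| Week 6 by readers | Final Outcome | Effect on New Adhesion rate |
|---|---|---|
| Adhesion | Undetermined | Lowers it if she is in the denominator; none if she is left out |
| No adhesion | No New Adhesion | Adds to the denominator only, so lowers it |

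She cannot enter the numerator on either branch. The SAP does not say whether Undetermined women count in the denominator. If there are no events at all, the rate is zero with or without her.

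**Step 3. Size, with assumed counts.** Take x new adhesions among n women clear at baseline, plus k women with baseline adhesion kept in the denominator. The rate is x/(n + k) instead of x/n.

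- x = 4, n = 40, k = 0: 4/40 = 10.0%.
- x = 4, n = 40, k = 5, all clear at Week 6: 4/45 = 8.9%.
- The same five women, all with adhesions at Week 6: 4/45 = 8.9% if Undetermined is counted in the denominator, 4/40 = 10.0% if it is not.

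**Step 4. Type 0 fibroid or polyp.** The Final Outcome rules do not restrict these women, so the direction is open. Assume they make up 10% of the set and the others have a 5% rate. The pooled rate is 0.9 × 5% + 0.1 × q, where q is their own rate:

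- q = 0%: 4.5%
- q = 5%: 5.0%
- q = 10%: 5.5%
- q = 20%: 6.5%

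**Step 5. Women in whom no fibroid qualifying under inclusion criterion 2 was ablated.** If a share f of the set were such women, and if their risk were zero, a rate p in the remainder would be reported as p × (1 − f). With p = 10%, f = 5% gives 9.5%, f = 20% gives 8.0% and f = 30% gives 7.0%. The SAP gives neither f nor any risk by fibroid type, so these figures show only how the result would depend on them.

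**The case against.** The strongest reply is that the set answers the question asked. The objective concerns "newly formed intrauterine adhesions after treatment with the Sonata System when used in women with submucous and/or transmural fibroids", which describes women by the fibroids they have, as inclusion criterion 2 does. Eligibility is screened at entry, reader-confirmed adhesion at both visits is kept out of New Adhesion, the Safety result is reported alongside, and the study is exploratory and descriptive with no hypothesis test.

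Much of this stands. No figure in the SAP is wrong, and the set does not contradict the objective. The Undetermined rule properly prevents an old adhesion from being counted as new. It guards one side only, however: the same woman still counts as No New Adhesion if she is clear at Week 6. The Safety analysis does not help either, because it keeps the same women. Nor does screening at entry, because exclusion criterion 1 rests on the investigator, so a woman can satisfy it as written and still have baseline adhesion on the readers' determination.

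A reader might infer three stronger points that the document does not support:

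- **That PP has no exposure condition.** It inherits receipt of study treatment. What it lacks is any condition on which fibroid was ablated.
- **That women with no qualifying fibroid ablated dilute the rate.** A separate line for "Number of ablated fibroids per subject" (4.6.5) shows that some fibroids may go unablated, not that the qualifying one does. Every treated woman also has transcervical intrauterine instrumentation, so near-zero risk cannot be assumed. Whether a type 4 fibroid qualifies depends on whether type 2-5 means one hybrid type or a range, which the SAP does not say.
- **That every breach of an exclusion lowers the rate.** The direction is fixed only for reader-confirmed baseline adhesion.

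**Conclusion.** The point holds as a defect in the definition of the primary set. PP is an evaluable-completer set that does not enforce eligibility. For women with reader-confirmed baseline adhesion the effect on the New Adhesion rate has one direction: down or none. That follows from the SAP's own classification rules and needs no assumption about risk.

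The size depends on how many such women are enrolled, which the SAP cannot tell us and which may be none. Five of them among 45 would turn 10.0% into 8.9%. For Type 0 or polyp breaches the direction is unknown. Dilution from women with no qualifying fibroid ablated is possible but hypothetical, and restricting the primary set on that ground would narrow the objective in a way that is open to debate. The correction should be made, but the study is descriptive and the point does not undermine it.

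**What to change.** In 4.6.1, extend the PP definition with words to this effect: *and who had no adhesion at baseline per the final independent-reader determination and did not breach inclusion criterion 2 or exclusion criterion 2*. The baseline condition must rest on the readers. Repeating exclusion criterion 1, which rests on the investigator, would not remove the women in question.

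Keep the Safety-population Final Outcome as the all-treated result, and list each woman removed by the new conditions with her Week 6 finding.

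Add one supplementary descriptive table of Final Outcome by whether a fibroid qualifying under inclusion criterion 2 was ablated. State there whether type 2-5 is one hybrid type or a range, and adjust 4.6.9.6, which at present declares subgroups not applicable.

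Renaming the set *evaluable* would settle the label but leave the one-sided classification in place.

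The cost is SAP wording, one derivation and one table. Fibroid type and ablations per fibroid are already summarised under 4.6.5, and the readers' baseline determination is already needed for 4.6.4.1. The downside is a slightly smaller PP denominator and possibly a slightly less favourable rate.
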